Study type & Phase	Basic science study involving procedures with human participants
Study design	Laboratory study/ Non-experimental confirmatory correlational research
Study Population/disease condition	Individuals diagnosed with heritable arrhythmic disorders and family members at risk of sudden cardiac death.
Eligibility criteria:	
Inclusion criteria:
 
 Participants will include patients diagnosed with a heritable arrhythmic disorder (including arrhythmogenic, hypertrophic and dilated cardiomyopathy, cardiac sarcoidosis as well as cardiac

	
channelopathies; Long QT syndrome, Brugada syndrome and catecholaminergic polymorphic ventricular tachycardia
 
 • Family members of victims of SCD evaluated for risk assessment and diagnosis. These groups include both individuals with clear disease manifestation (termed "affected") as shown by conventional diagnostic approaches (electrocardiography, echocardiography, cardiac MRI, Holter monitoring) as well as potential carriers of disease-causing mutations who, however, may not/not yet manifest any overt sign of cardiovascular abnormalities (termed "carriers"). These are typically family members of probands diagnosed with a heritable arrhythmic disorder or family members of a sudden cardiac death victim. • All individuals that fall in the above categories will be included regardless of their management (medication, devices, and surgical procedures). • Individuals with co-existing conditions will also be included and their medical history will be taken into account when interpreting the results of the immunohistochemical analysis. • Adult individuals (>18 years of age). • Pregnant women will be included as the approach used is not in any way harmful or uncomfortable. • All individuals must have provided the study team with a signed informed consent in order to participate in the study.
	
Exclusion criteria:
 
 • Children under 18 years of age • Individuals lacking decisional capacity. • Individuals with non-heritable, non-arrhythmic cardiac disorders (such as ischemic heart disease or inflammatory disorders) Non-English speakers will be excluded from the study unless a translator is present who can thoroughly explain to them the research question/plan in order for them to provide an informed consent.

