an informed consent form, a copy of which they will get to keep. If the sampling is taking place at home, the patient needs to return the signed consent form to City St George's, University of London along with their samples. If seen on site, the patient will then provide a study team member with 6 buccal smear samples. These samples will be transferred to [name] laboratory at City St George's, University of London. If using the at-home kit, the patient will obtain the buccal smears himself and then mail them to SGUL. The samples will be identified by a study ID number. There shall be no personal or medical information noted on them. Once at [name] laboratory at City St George's, University of London, they will be subjected to immunohistochemical analysis to characterize specific protein distribution. [name] and her lab team members will be blinded to the patient information. There shall be a single copy of a file linking the study ID number to a specific patient, accessible only by the patients' regular medical care providers.

Patients participating in the protein expression sub-study will provide a study team member with buccal cell samples to be transferred to [name] laboratory at City St George's, University of London. Such samples can only be obtained on-site and not by the patients themselves at-home.

Intervention plan and rationale

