All participants that are screened for inclusion into the study must be entered onto the Sponsor screening log JREOLOG0001 and will be assigned a unique study sequential number. Participants will be considered eligible for enrolment into this trial if they fulfil all of the inclusion criteria and none of the exclusion criteria as defined below.

Eligible participants will be entered onto the Sponsors Subject ID log JREOLOG0002 and assigned a unique study specific Identification number in a pre-agreed format in accordance with Site identifier and next sequential numerical value e.g. SG001

Inclusion criteria

- Participants will include patients diagnosed with a heritable arrhythmic disorder (including arrhythmogenic, hypertrophic and dilated cardiomyopathy, cardiac sarcoidosis as well as cardiac channelopathies; Long QT syndrome, Brugada syndrome and catecholaminergic polymorphic ventricular tachycardia).
- Family members of victims of SCD evaluated at the same clinic for risk assessment and diagnosis. These groups include both individuals with clear disease manifestation (termed "affected") as shown by conventional diagnostic approaches (electrocardiography, echocardiography, cardiac MRI, Holter monitoring) as well as potential carriers of disease-causing mutations who, however, may not/not yet manifest any overt sign of cardiovascular abnormalities (termed "carriers"). These are typically family members of probands diagnosed with a heritable arrhythmic disorder or family members of a sudden cardiac death victim.
- All individuals that fall in the above categories will be included regardless of their management (medication, devices, and surgical procedures).
- Individuals with co-existing conditions will also be included and their medical history will be taken into account when interpreting the results of the immunohistochemical or Western immunoblotting analysis.
- Adult individuals (>18 years of age).
- Pregnant women will be included as the approaches used is not in any way harmful or uncomfortable.
- All individuals must have provided the study team with a signed informed consent in order to participate in the study.

Exclusion criteria

- Children under 18 years of age
- Individuals lacking decisional capacity.
- Individuals with non-heritable, non-arrhythmic cardiac disorders (such as ischemic heart disease or inflammatory disorders).

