The data will be stored in TIF (images) format. The observations of the images will be logged on excel spreadsheets. City St George's, University of London is developing an institutional data repository as part of a Jisc-funded RDM Shared Service (April 2016 - September 2017). This will provide discoverability, secure storage and long-term preservation for all research data deposited in it. The PI will not have access to patient data/medical records. Slides will be labelled by a unique study participant ID code. There shall be no hard copy of the key linking the code to patients kept in the laboratory. There will be a linked document stored in the ISF JREOLOG0002. The study will be conducted in compliance with SOPs, GCP, all relevant laws of the EU and the UK including but not limited to: the Human Rights Act 1998, the Data Protection Act 1998, the Human Medicines Regulations 2012, ICH, the World Medical Association Declaration of Helsinki (2008), the NHS Research Governance Framework for Health and Social Care (2005). At the end of the study all coded samples shall be disposed of in accordance with the Human Tissue Authority's code of practice. Data generated will be kept on a password-protected workstation within a controlled-access office at City St George's, University of London. Computer softwares and firewall protection are up to date. City St George's, University of London servers are protected by line-interactive uninterruptible power supply (UPS) systems. No data will be kept in cloud-based storage. Only secure City St George's, University of London -controlled FTP servers will be used to share data with other team members. No sensitive data will be emailed according to ISO 27001. Digital data kept on City St George's, University of London servers are backed up overnight, every night, to hard disk and then cloned to tape storage. Full backups of all the data will be carried out monthly. The cloned tapes are stored separately in a fireproof and bombproof safe off-site. Laptops will be backed up and data removed from them as soon as practicable. This is in accordance with the City St George's, University of London Information Security and Removable Media policies: <https://portal.sgul.ac.uk/org/lis/computing-services/infosec-external>

Archiving arrangements

The trial essential documents along with the trial database will be archived in accordance with the sponsor SOP JREOSOP0016. The agreed archiving period for this trial will be 10 years.

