Both for the primary study (buccal smear immunostaining) and the sub-study (buccal cell western immunoblotting) only frequencies and associations will be assessed. No complex statistical analysis is required for completion of this study. Differences between disease groups in the distribution of immunoreactive signals and levels of protein expression will be assessed in a pairwise fashion with the Fisher exact test. Bonferroni correction will be used to correct P values because of multiple comparisons as appropriate. A p value of less than 0.05 will be considered significant. SPSS 21.0 software shall be used for all analyses. This statistical analysis will be performed by [name]. If expert statistical help is required, the research team will consult medical statisticians within St. George's University of London ([name] [name]) who shall not have access to the participants' personal information.

To describe the precise methods of analysis, I shall use ACM as an example. We have previously shown that in the hearts of patients with ACM a protein known as plakoglobin is dislocated from the cell-cell junctions regardless of the underlying pathogenic mutation or even in cases where no mutation has been identified but the clinical or pathological examination are consistent with a diagnosis of ACM. We used the "presence" or "absence" of plakoglobin from the cell junctions in the buccal mucosa to predict which individuals had ACM in a blinded fashion. Of 39 patient samples obtained, plakoglobin was absent from the cell junctions in 34. It was not, however, absent in samples from patients diagnosed with other forms of cardiomyopathy including hypertrophic, dilated or ischemic cardiomyopathy. This indicated that using plakoglobin distribution in the buccal mucosa as a means to diagnose ACM had sensitivity of 87.1% and specificity of 100%.

Secondary endpoint analysis

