- Research is not used to make decisions directly affecting individuals
- Short retention limits
- Restricted access controls
- Other (please specify)

Samples will be identified by a study ID number only. No personal data will be noted on the slides.

A key linking the study ID numbers to specific individuals will be kept in protected workstations at respective hospital sites only accessible by the participants' regular medical team.

How long will you need to hold the personal data for after the study has completed?

Not applicable

How will you make sure that you are holding data for the appropriate length of time and no longer?

Not applicable

How will the data be held /stored?

Personal data for all patients/family members are routinely held in medical files and electronically by the individuals' regular medical care providers. There shall not be shared with the principal investigator.

Will you be using any electronic and/or paper Case Report Forms (CRFs) to collect data? If so what are these and how will they be held securely and managed at the end of the project?

A data collection form, not including any personal data, will accompany each set of slides or cell suspension sample. This will include:

- The arrhythmia syndrome the participant has been diagnosed with

- Whether the participant has a family history of sudden cardiac death
- Whether the participant is taking any regular medication
- Whether the participant has been diagnosed with additional medical conditions
- Whether the participant is bearing a known disease-causing mutation
- The number of slides obtained (or if participating in the sub-study whether a single or double round of toothbrush rubbing was required to obtain sufficient cells)
- The team member obtaining the smears/cell sample (or the participant if using the at-home kit)

These will be completed by the participant's regular medical providers.

Following completion of the immunohistochemical/western immunoblotting analysis the principal investigator will complete the second part of the form with any changes observed in the distribution/expression levels of key proteins investigated.

There shall be no personal data noted on the form.

The forms will be held in [name] office at City St George's, University of London. The office is locked and accessible only by the PI.

Upon completion, they shall also be scanned and an electronic copy held in [name] St George's, University of London workstation accessible by the PI only.

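### Medical history may enter the interpretation of results with no rule limiting how, and the form that travels with the samples undercuts the blinding; selective use could inflate the accuracy estimates

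*Combined protocol and SAP*

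**What the plan says.** People with co-existing conditions are eligible. Section 7.1 adds that "their medical history will be taken into account when interpreting the results of the immunohistochemical or Western immunoblotting analysis"; the synopsis (section 3) has the same rule for the staining alone: "their medical history will be taken into account when interpreting the results of the immunohistochemical analysis".

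Section 14 sets a binary endpoint: each stain is present or absent, and each protein in the sub-study is control or reduced. Under Primary endpoint analysis, "Differences between disease groups in the distribution of immunoreactive signals and levels of protein expression will be assessed" by pairwise Fisher exact tests, with Bonferroni correction as appropriate. No stratum, covariate or exclusion for co-existing conditions is given. The entry for sensitivity analyses only points back to the preceding text.

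On blinding, section 6.1 says that the laboratory head "and her lab team members will be blinded to the patient information". Section 25 (Data Protection Impact Assessment), in the answer on case report forms, says: "A data collection form, not including any personal data, will accompany each set of slides or cell suspension sample". The participant's medical providers complete the first part. It covers the diagnosed syndrome, family history of sudden death, regular medication, known mutation and "Whether the participant has been diagnosed with additional medical conditions". After the laboratory work, "the principal investigator will complete the second part of the form with any changes observed".

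**The concern.** The sentence in sections 3 and 7.1 is the only stated handling of co-existing conditions, and it works result by result at someone's discretion. A result that fits the known diagnosis seldom calls for an explanation; one that does not fit invites one.

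The protocol supplies plausible explanations in both directions. The synopsis reports Cx43 remodelling in several cardiomyopathies, including ischemic, so an unexpected absent signal could be put down to another condition. Section 10.4 says Cx43 distribution recovers under effective anti-arrhythmic medication, so an unexpected present signal could be put down to treatment. Both effects may be real. That is a reason for a rule that applies whether or not the result fits the diagnosis.

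The means are also at hand. History and diagnosis arrive with the sample and sit on the form where the result is written. The roles statement at the front of the document gives sample analysis, data management and statistical analysis to one role. At stake are the accuracy figures that are the study's purpose. The year-one decision on recruiting channelopathy patients, which depends on whether status appears predictable, could be affected too.

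**Working it through.** **The texts together.** Sections 3 and 7.1 bring history into interpretation. Section 14 contains no step that changes or removes a call, but no statement that calls are final either. Section 6.1 blinds the laboratory to patient information. Section 25 sends diagnosis, medication, other conditions and mutation status with the sample, and nothing says the clinical part is withheld until the slide has been read. If the blinding means identity only, it does not cover diagnosis; if it covers clinical information, the form defeats it.

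**1. The plan's own figure.** Inputs (Primary endpoint analysis): 39 ACM samples, plakoglobin absent in 34, so 5 discordant.
Sensitivity = 34/39 = 87.18%. The printed 87.1% is this value truncated. Exact (Clopper-Pearson) 95% CI: 72.6% to 95.7%. The stated 100% specificity cannot be checked, because no comparator count is given.

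**2. Handling only the discordant results differently.** If *k* of the 5 are set aside, sensitivity is 34/(39 − *k*); if they are recoded as concordant, it is (34 + *k*)/39.

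| *k* | set aside | recoded |
|---|---|---|
| 0 | 34/39 = 87.2% | 34/39 = 87.2% |
| 1 | 34/38 = 89.5% | 35/39 = 89.7% |
| 2 | 34/37 = 91.9% (CI 78.1–98.3%) | 36/39 = 92.3% |
| 3 | 34/36 = 94.4% | 37/39 = 94.9% |
| 4 | 34/35 = 97.1% | 38/39 = 97.4% |
| 5 | 34/34 = 100% | 39/39 = 100% |

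The 91.9% at *k* = 2 equals the positive predictive value quoted in section 6.2 only by coincidence. That is a different quantity from a later series.

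**3. A range under assumed inputs.** Let *s* be true sensitivity, *h* the share with a co-existing condition (taken as equal among concordant and discordant results), and *e* the share of their discordant results explained away. With *d* = (1 − *s*)·*h*·*e*, apparent sensitivity is *s*/(1 − *d*) if those results are set aside and *s* + *d* if recoded. Assume *s* from 0.70 to 0.871, *h* from 0.2 to 0.4 and *e* from 0.25 to 1.
- Smallest: *d* = 0.129 × 0.2 × 0.25 = 0.00645. Set aside: 0.871/0.99355 = 87.7%. Recoded: 87.7%. Each is up 0.6 points.
- Largest: *d* = 0.30 × 0.4 × 1 = 0.12. Set aside: 0.70/0.88 = 79.5%, up 9.5 points. Recoded: 82.0%, up 12 points.

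**4. Specificity under assumed counts.** Take 100 unaffected people, 10 with absent signal, 5 of those 10 with a co-existing condition.
- As scored: 90/100 = 90.0% (exact CI 82.4% to 95.1%).
- Setting aside the 5: 90/95 = 94.7% (88.1% to 98.3%). The false-positive rate falls from 10% to 5/95 = 5.3%.

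Positive predictive value, TP/(TP + FP), rises for the same reason if true positives with a co-existing condition are kept.

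**5. Exclusion regardless of result, for comparison.** This depends on how common the condition is among the 90 true negatives.
- Half of them (45): 45/50 = 90.0%, no change.
- 15 of them (20 people with the condition in all): 75/80 = 93.8%, because here the condition goes with absent signal.

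**The case against.** The best defence is that the sentence is an eligibility bullet whose main job is to admit people with other illnesses. Taking history into account may mean no more than discussing confounding. Section 14 analyses calls as categorised and has no step for removing any. If the calls are analysed as scored, history changes no count. The form also collects other conditions for everyone, so history is not sought out only after a surprising result. All of this stands, and it limits the point to what could happen. It does not supply the missing rule.

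Three stronger readings are tempting and are not supported.
- *Accuracy is biased upward.* No text says that a result will be reclassified or dropped.
- *The rule contradicts section 12.4*, which says "The PI will not have access to patient data/medical records". It need not: the form supplies the history without access to records. The conflict that matters is between the form and the blinding in section 6.1.
- *Any distortion could never be undone.* Sections 12.2 and 12.4 keep the images, log the observations and require corrected form entries to stay readable, so reanalysis of the calls as scored should be possible if they are recorded as described.

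It is also fair to object that the specificity illustration uses assumed counts, and that part of a rise after exclusion can be genuine, as the 75/80 case shows. That favours exclusion by a preset list, blind to the result.

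**Conclusion.** The point holds as a defect in specification together with an internal conflict. The plan commits to using history in interpretation, sets no limits on that use, and sends the history and diagnosis to the person who records the result despite stated blinding. Inflation of sensitivity, specificity and positive predictive value is possible. Its occurrence and size cannot be shown from the documents.

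The figures show only what the discretion could do: 87.2% to 91.9% if 2 of the 5 discordant pilot results were set aside, and 90.0% to 94.7% for the assumed specificity case. Nothing suggests that any pilot result was treated this way. The upward direction assumes that history is applied mainly to discordant results; a preset rule applied without regard to the result would not produce this selective inflation. The plan should be changed, because the remedy is cheap and the aim is diagnostic accuracy.

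**What to change.** Replace the sentence on medical history in sections 3 and 7.1 with:

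> The present/absent (or control/reduced) call is made and locked before the clinical part of the form is released to the reader, and is not changed or set aside because of medical history. All participants with a result count as scored in the main analysis, except those who withdraw and ask for their results to be removed. One sensitivity analysis repeats it after excluding everyone with a pre-listed co-existing condition, whatever their result.

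The exception respects the withdrawal options in section 9.2. Reconcile sections 6.1 and 25 accordingly: the clinical part of the form should reach the reader only after the call is locked. The form now asks whether other conditions have been diagnosed; it should also record which ones, or the pre-listed exclusion cannot be applied.

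The cost is one extra form field, one extra table and a handling step for the form. Headline accuracy may come out slightly lower than under discretionary interpretation.

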9.3 Definition of the End of Trial

We define the End of the Trial as the day when the last buccal cell sample is obtained and analysed from a volunteer.

Study Procedures

Screening assessments

Participants will fall in either of the following three categories:

1. Patients already diagnosed with a heritable arrhythmic disorder (ACM, hypertrophic cardiomyopathy, dilated cardiomyopathy, Brugada syndrome, Long QT syndrome, catecholaminergic polymorphic ventricular tachycardia). The individuals will only be asked to participate in the study based on their already established diagnosis. No baseline screening assessment will be required.
2. Family members of patients diagnosed with a specific heritable arrhythmic disorder regardless of whether they show disease manifestation or not. These individuals will be asked to participate in the study based on the diagnosis of the proband. No further screening assessment will be required.
3. Family members of SCD victims. If pathology examination of the SCD victims' heart suggests that the individual has died due to a heritable arrhythmic disorder, when his/her family members attend the arrhythmic services at City St George's, University of London for medical evaluation/ risk stratification, they may be asked to participate at the study regardless of whether they show evidence of disease manifestation. No further screening will be required other than the clinical screening that is regularly offered to SCD victim relatives for risk stratification.

Baseline assessments

No baseline assessments are required after the participant has entered the study.

Interventions

The study participants will just be asked to open their mouth. A study team member will rub a soft brush a few times at the inside of their cheek and smear the brush on a microscopy slide. The slide will be sprayed with 70% ethanol to preserve the material and taken to the research laboratory. The patient will have a total of 6 smears taken (3 from each cheek). For the majority of the patients, only a single sampling will be enough which will take place during one of their regular follow-up appointments at the cardiology clinic. There is no pain and no discomfort associated with the procedure and it lasts only a few seconds.

If sampling is being done at-home, the participant will be provided with a kit containing two soft brushes, 6 microscopy slides, a small spray bottle with the fixative, and slide boxes. The

participant will then be asked to obtain the buccal smear samples following instructions on this youtube video: <https://www.youtube.com/watch?v=3hIHTaSuijs&feature=youtu.be>

Briefly, the participant will be asked to open the packaging of one sterile brush and open their mouth. The participant will then pass the brush several times at the inside of one cheek. The brush will then be smeared across a slide from one edge to the other and sprayed with the fixative 3 times from a distance of 20 centimeters. The slide will be left at room temperature for 1-2 minutes to dry, following which it can be placed in the slide box provided. This needs to be repeated 2 more times from the same cheek and then an additional 3 times from the other cheek for a total of 6 slides.

For those participating in the sub-study; they will be asked to open their mouth. A study team member will rub a toothbrush at the inside of their cheeks for 30 seconds. The toothbrush will then be placed in a tube of de-ionised water for the cells to be released and taken to the research laboratory. In the majority of the cases, a single collection will provide sufficient cell numbers. In selected cases, when not enough cells have been collected, we may need to rub the toothbrush against the cheek's inside for an additional 30 seconds.

Subsequent assessments

Regardless of the outcome of the baseline analysis, all participants will be asked to provide the study team members with additional samples up to 3 times/year following their appointment, using a self-sampling kit, and then at their next regular follow-up appointment. If the interim results yielding from the analysis of the self-obtained samples, shows abnormal protein distribution, the medical providers may contact the participant and discuss with them the possibility of bringing their next regular appointment forward for discussion and further evaluation. Regarding the sub-study, the majority of participants will only be asked to provide buccal cells once. In selected cases we may invite them to provide an additional sample at their next regular appointment. Our buccal smear work has shown that one protein in particular, Connexin43, shows restored distribution in response to clinically effective anti-arrhythmic medication. Yet, to date, we do not know what is the mechanism of action through which drugs fix Connexin43 localization and hence restore normal cardiac rhythm. Our sub-study would show whether the drugs act by increasing protein production or merely shifting the protein to junctional sites facilitating electrical conduction.

Methods

Laboratory procedures (if applicable)

The samples obtained will be mailed to [name] research laboratory. The fixed slide will be dipped in blocking buffer (97 ml phosphate buffered saline (PBS), 3 ml normal goat serum, 1 gram of bovine serum albumin and 150 microliters of Triton-X for a total of 100ml). The slides shall be left to incubate for 45 minutes at room temperature. The primary antibody will then be added (I use a liquid-repellent pen to draw a circle around the area where the cells are) diluted in blocking

buffer. For plakoglobin the optimal dilution is 1: 1500 and I use the mouse monoclonal antibody from sigma P8087. For Cx43 the optimal dilution is 1:1000 and the antibody is a rabbit polyclonal from Abcam ab11370. For desmoplakin the optimal dilution is 1: 50 and the antibody is a mouse monoclonal from Fitzgerald 10R-D109a. For PKP1 the optimal dilution is 1:20 and the antibody is a mouse monoclonal from santa cruz biotechnology sc-59880. Further protein targets/optimal dilutions will be assessed throughout the length of the study. The primary antibody stays on the slides overnight at 4 °C. The next day the slides will be equilibrated at room temperature for ~ 30 minutes, and washed 3 times (5 mins each) in PBS + 1% Triton-X. The secondary antibody is diluted in PBS (I use goat anti-mouse or anti-rabbit Cy3 conjugated antibodies from Jacksons ImmunoResearch at a dilution of 1:400) and the slides left in a covered box at room temperature for 2 hours. Following incubation with the secondary, again the slides are washed 3 times in PBS + 1% triton-X and mounted in mounting medium containing 4',6-Diamidino-2-Phenylindole, Dihydrochloride (DAPI).The immunostained slides will then be analysed by laser confocal microscopy at the Image Facility Core of City St George's, University of London.

No samples will be shipped outside [name] laboratory. Following imaging, the samples will be stored at a 4 °C fridge in [name] laboratory and they shall be safely discarded at the end of the study. All samples will be de-identified; there shall be no way to link a particular slide with a specific patient. No sample will be used for any further study other than the one described in the information sheet. A study ID log containing participants name and unique study identification number will be kept separately from any other information related to the study in the ISF. Any samples and test results will only bear the unique participant ID number. To ensure data confidentiality, only authorized persons will be granted access to study data, passwords and system IDs shall not be shared, physical security of the workstations/files will be maintained, adequate back-up plans will be in effect and staff will be trained on data entry systems and importance of security procedures. Only the participants' direct care team will have access to personal data or medical files throughout the duration of the study. Professional auditors and regulatory inspectors (NHS offices) may need to get access to participants' information to ensure the study is compliant with regulations. The participants will be informed of this possibility by their medical care providers, it shall be stated on the information sheet and they will consent to it as part of their informed consent.

For the sub-study: tubes containing the buccal cells will be transferred to [name] laboratory. The tubes will be centrifuged and the cell pellet will be rinsed with PBS. The solution will be centrifuged again, PBS will be discarded and the sample will be resuspended in 10mM Tris-HCl with 1% SDS. Cell lysis will be achieved by sonication (15 pulses, 40% power output, 30% duty cycle). Sonicated samples will be centrifuged at 4 degrees for 20 minutes and the supernatant transferred to a new tube. Protein concentration will be measured using a BCA assay. 20 micrograms of protein solution will be mixed with laemelli buffer, boiled at 95 degrees for 5 minutes and loaded on a Tris gel. It will then be subjected to electrophoresis (150 volts, 40 minutes). Proteins separated on the gel will be transferred on a nitrocellulose membrane, which will be incubated with an antibody against the protein of interest. Membranes will then be incubated with a suitable secondary antibody, washed and exposed with the aid of chemiluminescent reagents. Images will be obtained via a Chemidoc 18 software to be kept in [name] notebook. All

samples will be de-identified. There shall be no way to link a tube containing a participant's cells with his identity. No sample will be used for any further study other than the one described in the information sheet. A study ID log containing participants name and unique study identification number will be kept separately from any other information related to the study in the ISF. Any samples and test results will only bear the unique participant ID number.

Safety Events

Definitions

Adverse Event (AE)—any untoward medical occurrence in a participant whether it is considered to be related to the intervention or not, that includes a clinical sign, symptom, or condition and /or an observation of a near incident. (This does not include pre-existing conditions recorded as such at baseline; continuous persistent disease or a symptom present at baseline that worsens following administration of trial intervention

Serious Adverse Event (SAE)—any Adverse Event or untoward medical occurrence in a trial participant that can be wholly or partly to the intervention which resulted in any of the following:

- Results in death; or
- Is life-threatening (places the participant, in the view of the Investigator, at immediate risk of death)
- Requires hospitalisation or prolongation of existing hospitalisation (hospitalisation is defined as an inpatient admission, regardless of length of stay; even if it is a precautionary measure for observation; including hospitalisation for an elective procedure, for a pre-existing condition)
- Results in persistent or significant disability or incapacity (substantial disruption of one's ability to conduct normal life functions)
- Consists of a congenital anomaly or birth defect (in offspring of participants regardless of time of diagnosis).
- Or is another important medical condition

Important medical events that may not be immediately life-threatening or result in death or hospitalisation but may jeopardise the participant or may require intervention to prevent one of the outcomes listed in the definition of serious will also be considered serious.

